Study Protocol

Title: Effects of Heart Rate Oscillations During Meditation on Plasma Biomarkers of Alzheimer's Disease

NCT number: NCT06210035

IRB approval date: 5/25/2023

Uploaded date: 10/27/2025

Research Background

Cross-sectional studies suggest that meditation practices are associated with slower brain aging and improvements in early biomarkers of Alzheimer's disease (AD). However, the underlying mechanisms remain unclear. Most research has focused on the mental training aspects of meditation (e.g., paying attention to the present moment) and linked them to health outcomes. By contrast, the physiological changes that occur during meditation (e.g., heart rate oscillations, breathing rate) and their influence on health outcomes have been largely overlooked.

During some meditative practices, breathing slows down, which induces large oscillations in heart rate at the breathing frequency. In our previous HRV-ER trial (NCT03458910), a 4-week daily intervention designed to induce high-amplitude heart rate oscillations via slow-paced breathing significantly reduced plasma amyloid beta (A β)42 and A β 40 levels associated with AD.

Research Objectives

Based on our prior findings, the present study aims to separate out the mental training and physiological aspects of meditation to better understand their differential effects on plasma A β levels. We will examine how two types of meditation practices (with or without slow breathing) affect plasma A β levels compared with a no-intervention control group. We will also assess the effects of these practices on emotional well-being, given that various types of meditation improve well-being.

Healthy adults aged 18-35 who meet all eligibility criteria will be invited to this study. Participants will be asked to engage in one week of daily meditation practice or no-intervention control task at home. They will also be asked to visit the lab twice, once before and once after the intervention, to provide blood samples to assess plasma A β levels and to complete emotion questionnaires and memory tests.

Methods and Design

Lab Visit 1 (around 1.5 hours)

1) Consent

At the beginning of this visit, the researchers will provide detailed information about the study. Participants will then be asked to sign the consent form on DocuSign. When they sign, participants will have the opportunity to download a copy of the signed consent form for their record.

2) Administer questionnaires

Participants will be asked to complete the following questionnaires at the Emotion & Cognition Lab:

- Profile of Mood States (POMS)
- Depression Anxiety Stress Scales – Short Form (DASS-21)
- Five Facet Mindfulness Questionnaire
- Demographic information

3) Blood draw

Phlebotomists will collect blood samples up to 30 mL via venipuncture. Note that blood draw volume for blood donation in the US is 1 pint (~450 mL); thus, 30 mL should be safe for participants. Fasting is not required for the blood draw.

4) Measure resting heart rate

Give the participant devices and explain how to use them. The devices include a laptop with a customized meditation app, USB-module and an ear sensor that clips onto the earlobe and measures heart rate.¹). Using the devices, the participant will be asked to measure their heart rate for 5 min. During the 5-min resting state, they will be asked to sit in a chair with palms up, both feet flat on the floor, back straight, knees 90-degree angle, and closed eyes.

5) Paced breathing

Next, the app will ask participant to do 5 minutes of paced breathing at 15 breaths per minute by following audio cues. The participant will be asked to inhale when the ball ascends and exhale when it descends. This controlled breathing at around a normal breathing pace will allow us to assess baseline individual differences in heart rate spectral frequency with breathing rates controlled.

6) Intervention instructions

The app will randomly assign participant to one of the three conditions (belly-focus concentration meditation, belly-focus concentration meditation with slow breathing, no-intervention control). The experimenter will go over the instructions below and have them try the assigned practice for 20 minutes.

Instructions for the belly-focus meditation:

The app will show, "You will be asked to sit quietly to meditate for 20 minutes while your heart rate is recorded. During this time, you will listen to a guided meditation (pre-recorded by a meditation expert) to help you focus on the sensations around the belly. Please remember that it is normal for the mind to wander. When this happens, gently bring your attention back to your belly."

Audio guided meditation

At the beginning of the session:

- Welcome, please sit in a comfortable position in a chair or on a cushion with your back and neck upright and yet comfortable and gently close your eyes. If you wear glasses, feel free to take them off.
- Keep your mouth gently closed and focus your entire attention... entire attention on your belly.
- Remain aware, aware of every breath coming in, every breath coming out.
- On the inhale, allow your belly to receive your breath, on the exhale allow the belly to contract
- Notice the sensations around the belly as the breath comes in and out. As your breath flows in, feel it move down into your belly. Please observe how breathing makes your belly move. Whatever sensations arise, keep your attention here, noticing the arising and passing of sensation from moment to moment.
- As you inhale, feel your belly expanding and as you exhale feel your belly contracting. Noticing moment to moment whatever sensations are present here in the belly.
- As you meditate, many thoughts, feelings, images, and memories may come up. Welcome, all that arises. Letting them rise and fall, staying with the sensations of the breath expanding and contracting the belly.

At 5 minutes:

- If you find yourself in conversation with a thought or feeling, simply acknowledge this is happening, meet yourself kindly, and bring attention gently back to the sensations in the belly.

At 8 minutes:

- Whatever sensations arise, just observing. Observe how long the sensation lasts, how it changes with each passing moment. It may become stronger for some time, but sooner or later it passes away. No sensation is eternal, each arising and passing away. It is the same with any sensation, whether it be a tingling, an itching, warmth, coolness, or vibration, heaviness; simply observe whatever sensation is present, noticing how they change moment to moment.

At 12 minutes:

- It's quite normal for the mind to wander, if and when you notice your mind wandering, gently bring your attention back to the sensations of breath in the belly right here and now, what sensations are present?

At 15 minutes:

- Noticing where the mind is now, and gently bringing attention back to the sensations of breath and the belly. Moment to moment what sensations are

present in the belly. Each moment of the inhalation ... exhalation, what sensations are present now?

At the end:

- This is the end of the session. Close your practice by setting an intention to stay connected to your body as you move slowly out of the meditation.

Instructions for the belly-focus meditation with slow breathing:

The app will show, "You will be asked to sit quietly to meditate for 20 minutes while your heart rate is recorded. During this time, you will listen to a guided meditation (pre-recorded by a meditation expert) to help you focus on the sensations around the belly. You will also be asked to breathe slowly during the entire meditation session. Please remember that it is normal for the mind to wander. When this happens, gently bring your attention back to the upper lip area."

Audio guided meditation

At the beginning of the session:

- Welcome, please sit in a comfortable position in a chair or on a cushion with your back and neck upright and yet comfortable and gently close your eyes. If you wear glasses, feel free to take them off.
- Keep your mouth gently closed and focus your entire attention... entire attention on your belly.
- Remain aware, aware of every breath coming in, every breath coming out.
- On the inhale, allow your belly to receive your breath, on the exhale allow the belly to contract.
- Take long slow breaths as I guide you. Inhale for a count to 5 and exhale for a count to 5. Breathe slowly and gently at this pace during the entire meditation exercise. I'll count with you for the first few breaths. Then you can count on your own. Inhale, 2, 3, 4, 5, exhale 2, 3, 4, 5. Inhale, 2, 3, 4, 5, exhale 2, 3, 4, 5. Continue breathing this way on your own.
- Notice sensations around the belly as the air moves in and out. As your breath flows in, feel it move down into your belly. Please observe how breathing makes your belly move. Whatever sensations arise, keep your attention here, noticing the arising and passing of sensation from moment to moment.
- As you inhale, feel your belly expanding and as you exhale feel your belly contracting. Noticing moment to moment whatever sensations are present here in the belly.
- As you meditate, many thoughts, feelings, images, and memories may come up. Welcome, all that arises. Letting them rise and fall, staying with the sensations of the breath expanding and contracting the belly.

At 5 minutes:

- If you find yourself in conversation with a thought or feeling, simply acknowledge this is happening, meet yourself kindly, and bring attention gently back to the sensations in the belly. Remember to breathe slowly and gently for a count of 5 while inhaling and a count of 5 while exhaling.

At 8 minutes:

- Whatever sensations arise, just observing. Observe how long the sensation lasts, how it changes with each passing moment. It may become stronger for some time, but sooner or later it passes away. No sensation is eternal, each arising and passing away. It is the same with any sensation, whether it be a tingling, an itching, warmth, coolness, or vibration, heaviness; simply observe whatever sensation is present, noticing how they change moment to moment. Remember to breathe slowly and gently for a count of 5 for each inhalation and a count of 5 for each exhalation during the remaining session.

At 12 minutes:

- It is normal for the mind to wander, if and when you notice your mind wandering, gently bring your attention back to the sensations in the belly right here and now, what sensations are present? Remember to breathe slowly and gently.

At 15 minutes:

- Noticing where the mind is now, and gently bringing attention back to the sensations of breath and the belly. Moment to moment what sensations are present in the belly. Each moment of the inhalation ... exhalation, what sensations are present now?

At the end:

- This is the end of the session. Close your practice by setting an intention to stay connected to your body as you move slowly out of the meditation.

Instructions for the no-intervention control condition:

The app will show, "You will be asked to sit quietly for 20 minutes while your heart rate is recorded. Please feel free to do whatever you would like to do (e.g., use your phone or computer, read a book, watch TV, listen to music) as long as your activity does not involve head motion."

Before each practice session, participants in all conditions will view 6 images from the Nencki Affective Picture System (NAPS; uploaded on section 21.2) and rate them on a scale of 1-9 (1 = very negative to 9 = very positive, with 5 = neutral). At the post-intervention lab visit (i.e., Lab Visit 2), they will be given memory tests for these images (see below for more details).

One week intervention at home

Participants will be asked to engage in the assigned practice for 40 minutes (20 min x two times) each day for a week.

Lab Visit 2 (around 1 hour)

Participants will be asked to return their devices and complete the assessments listed in Lab Visit 1 Steps 2-5. In addition, participants will complete a free recall test in which they will describe as many images as they can that were viewed right before each meditation practice in the past week. They will also complete a recognition memory test in which they will be given 3 response options for each image; Remember, Know and New (Remember = "I vividly remember," Know = "I have a sense of familiarity with the image, New = the image was not seen before").

Statistical Analysis Plan (SAP)

Study Title	Effects of Heart Rate Oscillations During Meditation on Plasma Biomarkers of Alzheimer's Disease
Principal Investigator	[name] Professor of Gerontology, Psychology and Biomedical Engineering University of Southern California Los Angeles, California, USA
Protocol Identification Number	UP-23-00373
ClinicalTrials.gov Identifier	NCT06210035
Author	[name] Research Associate [name] of Southern California Los Angeles, California, USA
Version	Draft 1.0
IRB Approval Date	5/25/2023

1. Objectives and hypotheses

The aim of the study was to examine how two types of meditation practices (with or without slow breathing) affect plasma A β levels of compared with a no-intervention control group. In addition, we examined the effects of the two types of meditation practices on emotional well-being relative to the control group.

We predicted that meditation with slow breathing would increase heart rate oscillations during practice, leading to greater reductions in plasma A β levels relative to the other conditions. In addition, we hypothesized that both meditation practices would improve emotional well-being compared with the control condition.

2. Sample Size & Power consideration

For plasma A β , we estimated reliability using correlations between pre- and post-intervention time points in the HRV-ER trial. Effect sizes were derived from the pre-post difference in the younger adult slow-paced breathing group of HRV-ER. We powered the study to detect small-to-medium effect sizes ($f = 0.2$) with a 0.459 correlation among repeated measures, aiming for 80% power at $\alpha = .05$. Based on these parameters, a total sample size of $N = 72$ (with two assessments) was required. Based on the HRV-ER study, we estimated a 12% dropout rate ($72 \times 12\% \approx 9$). Thus, we planned on a total enrollment of $N = 81$ ($72+9$) to achieve a final $N = 72$ for analyses. Ultimately, 89 participants completed the study.

3. Outcome Measures and Analyses

We examined condition differences in intervention-related change in the following outcome measures. The average time between pre- and post-intervention assessments was one week.

Primary outcome measures

- **Change in plasma amyloid beta levels:** We computed an aggregate score based on plasma A β 40 and A β 42 levels (pg/mL), calculated as the average of their Z-scores. Higher values on this composite measure are associated with greater risk of Alzheimer's disease. We conducted a 2 (time: pre, post) \times 3 (condition: meditation with slow breathing, meditation without slow breathing, no intervention control) ANOVA to test for a time \times condition interaction in plasma A β levels, assessing group differences in change over time.
- **Change in plasma Ab42/40 ratio:** We conducted a time X condition ANOVA with plasma Ab42/40 ratio scores as the dependent variable (to assess group differences in change). The ratio was calculated by dividing the plasma Ab42 concentration (pg/ml) by the plasma Ab40 concentration (pg/ml).

Secondary outcome measures

- **Change in plasma pTau-181/tau ratio:** We conducted a time X condition ANOVA with plasma pTau-181/total Tau ratio scores as the dependent variable (to assess

group differences in change). The ratio was calculated by dividing the plasma pTau-181 concentration (pg/ml) by the plasma total Tau concentration (pg/ml).

- **Change in emotional well-being:** We conducted a time X condition ANOVA with emotional well-being as the dependent variable (to assess group differences in change). Emotional well-being was measured by the Profile of Mood States (POMS), which consists of 40 items that are rated on a 5-point scale ranging from "0=not at all" to "4=extremely. Total Mood Disturbance (TMD) was calculated by summing the totals for the negative items and then subtracting the totals for the positive items. A constant (i.e., 100) was added to the TMD formula to eliminate negative scores. Higher scores indicate more negative mood states. The scores range from 56 and 216.

Safety outcomes

Three non-serious adverse events were reported and subsequently resolved.

4. Populations and subgroups to be analyzed

Population analyzed is composed by all randomized subjects who completed assessments and whose data quality was sufficient for data analysis.

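### The plasma A-beta time × condition ANOVA is valid but leaves baseline unused as a covariate; at the SAP's own planning correlation of 0.459, ANCOVA would cut arm-contrast variance by about 27%

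*SAP*

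**What the plan says.** SAP section 3 analyses the composite of A-beta 40 and A-beta 42 with a 2 × 3 ANOVA and tests the time × "condition interaction in plasma A β levels, assessing group differences in change over time". The other outcomes (Ab42/40, pTau-181/total tau, POMS) get the same model. Baseline enters only as the first level of time. Neither document names a covariate.

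SAP section 2 says of plasma A-beta that "we estimated reliability using correlations between pre- and post-intervention time points in the HRV-ER trial", and the power calculation uses a "0.459 correlation among repeated measures". The Protocol's Research Background describes HRV-ER as "a 4-week daily intervention designed to induce high-amplitude heart rate oscillations via slow-paced breathing". In the present trial, by contrast, "The average time between pre- and post-intervention assessments was one week" (SAP section 3).

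In the Protocol's Lab Visit 1, questionnaires and the blood draw are steps 2 and 3. Assignment comes at step 6: "The app will randomly assign participant to one of the three conditions".

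The SAP is written after the event. Section 2 ends "Ultimately, 89 participants completed the study", and section 3 reports analyses in the past tense, for example "We conducted a time X condition ANOVA with plasma Ab42/40 ratio scores as the dependent variable".

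**The concern.** A change score subtracts the whole baseline value, which fixes the baseline slope at 1. With equal SDs and a pre-post correlation of 0.459, the best-fitting slope is about 0.46. Subtracting more than the data support adds baseline noise to every arm contrast. It also over-corrects for chance imbalance: an arm that starts high by chance will tend to show a larger fall.

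Baseline blood and questionnaires precede assignment, so the baseline value is a legitimate covariate. ANCOVA would estimate the slope from data the trial already holds. At stake is the width of the intervals on a primary outcome and their sensitivity to chance imbalance with about 30 people per arm. The validity of the existing test is not at stake.

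**Working it through.** **Inputs.** From SAP section 2: f = 0.2, correlation ρ = 0.459, α = 0.05, target power 80%, required N = 72, 89 completers. Assumed because the documents do not say: arms of near-equal size (30/30/29), all 89 analysable, and equal pre and post SDs except where varied below.

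**1. The SAP's own N.** The SAP gives no formula. For the two-visit interaction with three arms, the noncentrality f²·(N−3)·2/(1−ρ) gives 0.04 × 69 × 2/0.541 = 10.20 at N = 72. Power on F(2, 69) is 80.6%, and 72 is the smallest balanced N that reaches 80%. The common alternative, f²·N·2/(1−ρ), gives N = 69, with 82.3% at N = 72; an unrounded f of 0.195 to 0.198 would then also lead to 72 in equal arms. The first form is used below because it returns the SAP's figure from its printed inputs.

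**2. Variance ratio, equal SDs.** In units of σ², the variance factor is 2(1−ρ) for change and 1−ρ² for ANCOVA. The ratio is (1−ρ²)/[2(1−ρ)] = (1+ρ)/2. At ρ = 0.459 this is 0.7893/1.082 = 0.7295, a 27% cut. Estimating the slope costs a factor 1 + 1/(N−5): the net ratio is 0.740 at N = 72 and 0.738 at N = 89. The SE is then √0.738 = 0.86 of its change-score value.

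| ρ | Ratio | Variance cut | Power at N = 89, ANOVA | Power at N = 89, ANCOVA (net) |
|---|---|---|---|---|
| 0.3 | 0.65 | 35% | 79.4% | 93.5% |
| 0.459 | 0.73 | 27% | 89.1% | 96.3% |
| 0.6 | 0.80 | 20% | 96.3% | 98.7% |
| 0.8 | 0.90 | 10% | >99.9% | >99.9% |

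The power columns divide the noncentrality by the net ratio and use F(2, N−4) for ANCOVA. They matter only if ANCOVA is the primary test. At N = 72 and ρ = 0.459 the pair is 80.6% and 91.2%.

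**3. Unequal SDs.** With s = post SD/pre SD, the ratio is s²(1−ρ²)/(1 + s² − 2ρs).
- ρ = 0.459, s = 0.8: 0.5052/0.9056 = 0.558, a 44% cut.
- ρ = 0.459, s = 1.25: 1.2333/1.415 = 0.872, a 13% cut.
- ρ = 0.8, s = 1.25: 0.5625/0.5625 = 1.00, no gain.

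**4. Interval width at N = 89** (29.67 per arm on average).
- Change score: 1.988 × √(1.082 × 2/29.67) = 0.54 SD.
- ANCOVA: 1.988 × √(0.7893 × 2/29.67 × (1 + 1/84)) = 0.46 SD.

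**5. Chance imbalance.** One SE of the baseline difference between two arms is √(2/29.67) = 0.26 SD. The change-score contrast shifts by (1 − 0.459) × 0.26 = 0.14 SD in the opposite direction. ANCOVA removes this shift.

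**6. Simulation** (20,000 trials per cell, ρ = 0.459). Power was 80.7% vs 91.1% at N = 72 and 88.9% vs 96.2% at N = 89. Mean half-widths at N = 89 were 0.537 and 0.461 SD. Type I error for both tests was 4.8% to 5.3% over ρ from 0.3 to 0.8.

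No correlation is given for Ab42/40, pTau-181/tau or POMS, so no gain can be computed for them.

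**The case against.** The best defence is that nothing in the primary result is wrong. The interaction test is valid, answers the stated question about change, and matches the power calculation. With 89 completers it exceeds its 80% target if all are analysable and the planning values hold. The study is finished, so ANCOVA would probably be only an added sensitivity analysis, and a second model after the fact increases analytic flexibility. This is right about validity and likely about timing. It is why the ANOVA should stay primary if outcomes had been seen. It does not remove the gain in interval width or the adjustment for chance imbalance.

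A second objection is that the size of the gain is borrowed. The 0.459 is from a 4-week trial; the SAP names the younger adult group only for the effect size and does not say which age group or A-beta measure the correlation describes. This stands: 27% is the value at the SAP's own planning figure, and a higher one-week correlation would shrink it.

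A third is that the power figures depend on the noncentrality convention and on assumed arm sizes. With f²·N the pairs become 82.3% vs about 92% (N = 72) and 90.1% vs 96.8% (N = 89), and the ANOVA figure at ρ = 0.3, N = 89 becomes 80.8%. The gain stays at about 10 and 7 points. SAP section 4 restricts analysis to adequate data, so the analysed N may be below 89. The variance ratio before the small slope cost depends on neither choice.

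**Conclusion.** The concern holds as a loss of precision on a primary outcome. At ρ = 0.459 and equal SDs, ANCOVA lowers the variance of an arm contrast by 27% (26% after the slope cost) and the SE by about 14%. Over the ranges examined the gain runs from 44% to nil, depending on this trial's one-week correlation and SD ratio, neither of which the documents give.

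The past-tense reporting makes it likelier that outcomes had been seen by condition before any model could now be added. In that case the benefit is narrower intervals and adjustment for chance imbalance, not higher power of the primary test. The power gain applies only if the outcomes had not been seen. The saving in sample size (smallest balanced N for 80% power of 57 net, or 54 before the slope cost, against 72) is of planning interest only, since enrolment is over.

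**What to change.** For each outcome, regress the post value on condition and the baseline value of the same outcome. Report arm contrasts with 95% CIs, with the existing time × condition ANOVA beside them.

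State in the SAP whether outcomes had been seen by condition when the model was chosen. If they had not, name ANCOVA primary and the ANOVA a sensitivity analysis. If they had, keep the ANOVA primary and label ANCOVA a post hoc sensitivity analysis.

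Report this trial's own pre-post correlation and SDs for each outcome, so that the actual gain is visible. Because the SAP does not state the reference for the composite's Z-scores, standardise both visits against one common reference, so that change is measured on a single scale.

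The cost is one extra model and one degree of freedom per outcome, with no new data. The real cost is candour in labelling: a model added after outcomes were seen by condition must be declared post hoc.

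### Section 1 of the SAP makes arm-specific predictions for Aβ and mood, but section 3 tests each only with the three-arm time × condition interaction and names no contrast

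*SAP*

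**What the plan says.** SAP section 1 gives two predictions, each with arms, comparators and a direction. Slow-breathing meditation should produce larger falls in Aβ "levels relative to the other conditions", and "both meditation practices would improve emotional well-being compared with the control condition". The protocol (Research Objectives) says that the study "aims to separate out the mental training and physiological aspects of meditation".

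SAP section 3 assigns one test to each outcome. For the Aβ composite it is a 2 × 3 ANOVA testing the time × condition interaction, "assessing group differences in change over time". For mood it is a "time X condition ANOVA with emotional well-being as the dependent variable". The scales are clear: "Higher values on this composite measure are associated with greater risk" for the composite and "Higher scores indicate more negative mood states" for POMS Total Mood Disturbance, so a fall is the favourable direction on both.

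Neither document names a planned contrast, a pairwise or post hoc comparison, or a multiplicity rule for comparing arms. The protocol has no statistical section that could supply one.

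**The concern.** With three arms and two time points, the interaction has 2 numerator degrees of freedom and no direction. It asks whether mean change differs anywhere among the arms. The section 1 predictions are narrower: slow breathing below each of two comparators for Aβ, and each of two meditation arms below control for mood.

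The Aβ case matters most. Slow-breathing against non-slow meditation is the only pair of arms that holds meditation constant and varies the breathing. A significant interaction is equally likely, for the same f, whether slow breathing is the active element or meditation works equally well with and without it. For mood, it can arise when only one practice helps, in which case the prediction about both is false. If the interaction alone is reported, either prediction could be claimed on evidence that does not bear on it.

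**Working it through.** **Inputs.** From SAP section 2: f = 0.2, correlation between repeated measures 0.459, α = 0.05, two assessments, N = 72, and 89 completers. Assumed: equal allocation (24 per arm; the ratio is not stated), f read as a between-arm interaction effect, and the patterns of arm means below. The reading of f needs stating because "Effect sizes were derived from the pre-post difference in the younger adult slow-paced breathing group" of the earlier trial, which is not a between-arm contrast.

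**The plan's own figure.** For the interaction, λ = f²·N·m/(1 − ρ), with 2 and N − 3 degrees of freedom and m = 2. At N = 72, λ = 0.04 × 72 × 2 / 0.541 = 10.65 and power is 82.3%. The smallest N reaching 80% is 69 (80.5%), so 72 is not reproduced exactly but is slightly conservative. Rounding up to a multiple of 6 gives 72. Nothing below depends on this gap. At N = 89, power is 90.1%.

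**Change-score scale.** The SD of change is √(2 × 0.541) = 1.040 raw SD. On that scale f becomes 0.2 × √(2/0.541) = 0.385. If one arm differs from two equal arms by d, the SD of the three means is d√2/3, so d = 0.385/0.471 = 0.816 change SD. The following results simulate change scores (400,000 runs per case, pooled error, two-sided 0.05, predicted sign required).

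**Aβ, both meditation arms fall equally (no added effect of slow breathing), 24 per arm:**

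| f | Interaction significant | Slow significantly better than both comparators, among those |
|---|---|---|
| 0.10 | 28% | 6.6% |
| 0.15 | 56% | 4.1% |
| 0.20 | 82% | 3.0% |
| 0.25 | 96% | 2.6% |

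At f = 0.20 the unconditional rate is 0.823 × 0.030 = 0.025, the error expected of a two-sided 5% test in one direction. Requiring the contrasts therefore controls the false claim; the interaction does not.

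**POMS, only one meditation arm improves.** The SAP gives no f or correlation for mood, so both are assumed here. The interaction is significant in:

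| Assumed f | ρ = 0.459 | ρ = 0.30 |
|---|---|---|
| 0.10 | 28% | 22% |
| 0.15 | 56% | 45% |
| 0.20 | 82% | 71% |
| 0.25 | 96% | 89% |

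At f = 0.20 and ρ = 0.459, both meditation arms are significantly better than control in about 3% of the significant trials.

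**Power for the joint Aβ claim (slow better than both comparators).**
- Only the slow arm changes: 0.684 at N = 72, or 0.676 if a significant interaction is also required. At 30/30/29 with the interaction required: 0.791.
- Meditation alone has half the effect, f held at 0.2 (slow shift 0.942 change SD), interaction required: 0.352 at N = 72.
- Same pattern with the slow shift fixed at 0.816 (f then 0.173), interaction required: 0.266 at N = 72.

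**Error control.** With no true differences, unadjusted pairwise tests carried out only after a significant interaction give a family-wise error of 0.049 within one outcome. If exactly one pair of arms is equal, only one true null pairwise comparison remains, and it is tested at 5%.

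**The case against.** An overall test followed by pairwise comparisons is ordinary practice, and a short SAP may leave the second step implicit. A reader might go further and infer that slow-breathing against non-slow meditation was never tested. The documents do not support that: the comparison contributes to the 2-df interaction, and silence shows only that no follow-up was named. The gap stands all the same, because which pairs, whether both are required, and how alpha is handled are all left open.

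The Aβ prediction can also be read as slow breathing against the other two arms combined. That contrast has 89.6% power at N = 72 if only slow breathing works, and the authors may choose it. Section 3 does not name it either, and it would not by itself separate slow breathing from meditation.

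A reader might infer that the mood interaction would usually be significant when only one practice helps. That depends on values the SAP ties to plasma Aβ; at an assumed f of 0.10 it is significant in only 22% to 28% of trials.

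Finally, the SAP reports its analyses in the past tense, so contrasts added now cannot restore prespecification. That is true, and it limits the benefit to clearer and better-supported reporting. Section 1 does record the arms, comparators and direction of the two hypotheses.

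**Conclusion.** The point holds and should be fixed. The text is unambiguous: two arm-specific, directional predictions in section 1, and one non-directional interaction per outcome in section 3. The interaction result remains valid for the question it asks, but neither prediction can be claimed from it alone.

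The Aβ percentages illustrate the size of the problem and rest on equal allocation, on f as a between-arm effect, and on assumed patterns of means. The mood percentages rest on wholly assumed inputs. Confidence is high in the textual gap and lower in any single percentage.

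A reader might extend the point to the Aβ42/40 and pTau-181/tau ratios, which are also tested only by the interaction. Section 1 states no explicit prediction for either ratio, so no mismatch is claimed there.

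**What to change.** Add named contrasts of change to SAP section 3 and to the report.

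- **Aβ composite:** slow-breathing against non-slow meditation, and slow-breathing against control, both required with slow breathing lower, to claim the section 1 prediction. Add non-slow meditation against control for the mental-training component.
- **POMS Total Mood Disturbance:** each meditation arm against control, both required with meditation lower, to claim that both practices help.
- **Alpha:** when both contrasts are required, the joint claim needs no preliminary test or adjustment. For claims from a single contrast, either proceed only after a significant interaction or use planned contrasts directly with a stated adjustment. Both are valid. The first reduces single-contrast power from 80% to 75% at N = 72 when only the slow arm changes.
- **Label:** describe the contrast tests as not shown to be prespecified in these documents. The label applies to the tests, not to the section 1 hypotheses.

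No change is proposed for the two ratios.

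The cost is a few lines of text and analysis, plus an honest loss of power for the stronger claim. If only the slow arm changes, the joint Aβ claim has about 68% power at N = 72, against 82% for the interaction. It has about 79% at N = 89, provided that every completer is analysable and the split is 30/30/29; section 4 restricts the analysis to data of sufficient quality and gives no analysed number. If meditation alone has half the effect, joint power at N = 72 is about 35% with f held at 0.2, or 27% with the slow-arm shift held fixed. A non-significant joint result should be reported with that limit in view.
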